### Table 3: RECIST/bone lesion Assessments Visit Windows

(W: Week)

Week Number	Days after first dose of the treatment (Cycle 1 Day 1)	Visit Label	Window	Visit Window
8	57	W8		[Day 50; Day 84]
16	113	W16		[Day 85; Day 140]
24	169	W24		[Day 141; Day 196]
32	225	W32		[Day 197; Day 252]
40	281	W40		[Day 253; Day 308]
48	337	W48		[Day 309; Day 364]
56	393	W56		[Day 365; Day 434]
68	477	W68		[Day 435; Day 518]
80	561	W80		[Day 519; Day 602]
92	645	W92		[Day 603; Day 686]
104	729	W104		[Day 687; Day 770]
....	....	....		.....
Until RECIST 1.1 progression				

**4.3.3 Handling Missing Data**

In general, other than for the below described, or where otherwise specified in the particular analysis, missing data will not be imputed and will be treated as missing.

**4.3.3.1 Imputation of Adverse event and Concomitant medication.**

- Missing day: impute with the 1st of the month unless month and year are same as month and year of first dose of study treatment then impute with first dose date.
- Missing day and month: impute with 1st January unless year is the same as first dose date then impute with first dose date.
- Completely missing: impute with date of first dose of study treatment, unless the end date suggests it could have started prior to this in which case impute with 1st January of the same year as the end date.

When imputing a start date ensure that the new imputed date is sensible i.e. is prior to the end date of the AE or medication.

**4.3.3.2 Imputation of Adverse Event and concomitant medication end date.**

- Missing day: impute with the last day of the month, unless month and year are the same as month and year of last dose of study treatment, then impute with the last treatment date in that month.

- Missing day and month: impute with 31st of December unless the year is the same as the year of last dose of the study treatment, then impute with the last treatment date of that year.
- Completely missing: assume the event is still ongoing and do not impute any date if it is flagged as “ongoing”.

Generally, the imputation of dates is to decide if an observation is for AEs or concomitant for medications. Flags will be retained in the database indicating where any programmatic imputation has been applied, and in such cases, durations and study days will not be calculated.

#### 4.3.3.3 Imputation for Laboratory Values Outside of Quantification Range

Values of the form of “< x” (i.e., below the lower limit of quantification) or > x (i.e. above the upper limit of quantification) will be imputed as “x” in the calculation of summary statistics but displayed as “< x” or “> x” in the listings. Values of “<=x” or “>=x” will be imputed similarly.

#### 4.4 Software

All report outputs will be produced using SAS®[4] version 9.4[5] or later in a secure and validated environment.

#### 4.5 Analysis Data Sets

##### 4.5.1 Module 1

Details of all analysis sets defined for Module 1 are presented in [Table 4](#).

**Table 4: Analysis set**

Analysis set	Definition
Enrolled analysis set	All study participants who signed the informed consent form (including screening failures).
Evaluable for response set	Cohort A: All study participants with measurable baseline disease who received at least 1 dose of study intervention.  Cohort B: All study participants with measurable disease and/or unfavourable CTC count at baseline who received at least 1 dose of study intervention.
[a] Molecularly eligible centrally confirmed set	All molecularly eligible and centrally confirmed participants who received at least 1 dose of study intervention.

[a]Molecularly eligible centrally confirmed evaluable for response set
	
Cohort A: All molecularly eligible and centrally confirmed study participants with measurable baseline disease who received at least 1 dose of study intervention.
 
Cohort B: All molecularly eligible and centrally confirmed study participants with measurable disease and/or unfavourable CTC count at baseline who receive at least 1 dose of study intervention.

CCI [REDACTED]
	
CCI [REDACTED]

CCI [REDACTED]
	
CCI [REDACTED]

Safety set
	
All participants who received at least 1 dose of study intervention.

Interim analysis set
	
All participants in the molecular eligible centrally confirmed evaluable for response set with a chance to have at least two follow up RECIST assessments (i.e. all patients who received first dose of ceralasertib, at least 16 weeks prior to the data cut off date).

[a] Please refer to the latest CSP for more details regarding central confirmation. A separate specification document will be provided to support the programming of the ‘centrally confirmed’ flag.

Upon database release, protocol deviation and analysis set outputs will be produced and will be sent to AZ for review. Prior to database lock, analysis set classification meeting will be arranged to discuss the outputs and decide which participants and/or participant data will be excluded from certain analyses. Decisions made regarding the exclusion of participants and/or participant data from analyses will be made prior to database hard lock and will be documented and approved by AZ.

A summary on which analysis set will be used for each outcome variable is provided in [Table 5](#) (Cohort A) and [Table 6](#) (Cohort B).

**Table 5: Summary of outcome variables and analysis sets for Cohort A**

Outcome Variable	Analysis Set
Study Population/Demography Data	
Disposition of participants	All Enrolled

# Parexel International

AstraZeneca

D5339C00001

Statistical Analysis Plan

Outcome Variable	Analysis Set
Demography characteristics	Safety set
Baseline and disease characteristics	Safety set
Important protocol deviations	Safety set
Medical/surgical history	Safety set
Previous anti-cancer therapy	Safety set
Previous radio therapy	Safety set
Concomitant medications/procedures/radiotherapy	Safety set
Efficacy Data	
ORR/BoR	Molecularly eligible centrally confirmed evaluable for response set Evaluable for response set Interim analysis set*
Duration of response	Molecularly eligible centrally confirmed evaluable for response set Evaluable for response set‡ Interim analysis set*
Percentage change in tumour size	Molecularly eligible centrally confirmed evaluable for response set Evaluable for response set◊ Interim analysis set*
PFS	Molecularly eligible centrally confirmed set Safety set Interim analysis set*
CCI [REDACTED]	
CCI [REDACTED]	CCI [REDACTED]
Safety Data	
Exposure	Safety set
AEs	Safety set
Laboratory measurements	Safety set
Vital signs	Safety set
ECG	Safety set
Physical examination	Safety set

# Parexel International

AstraZeneca

D5339C00001

Statistical Analysis Plan

Outcome Variable	Analysis Set
Eastern Cooperative Oncology Group performance status (ECOG PS)	Safety set

‡ Only swimmer plot will be provided for this analysis set.

◇ Only spider plot will be provided for this analysis set.

\*This analysis set will be used only for interim analysis summary.

**Table 6: Summary of outcome variables and analysis sets for Cohort B**

Outcome Variable	Analysis Set
Study Population/Demography Data	
Disposition of participants	All Enrolled
Demography characteristics	Safety set
Baseline and disease characteristics	Safety set
Important protocol deviations	Safety set
Medical/surgical history	Safety set
Previous anti-cancer therapy	Safety set
Previous radio therapy	Safety set
Concomitant medications/procedures/radiotherapy	Safety set
Efficacy Data	
Composite response rate	Molecularly eligible centrally confirmed evaluable for response set Evaluable for response set Interim analysis set i
Duration of composite response	Molecularly eligible centrally confirmed evaluable for response set Evaluable for response set‡ Interim analysis set i
Percentage Change in tumour size	Molecularly eligible centrally confirmed evaluable for response set Evaluable for response set◇ Interim analysis set i
Radiological ORR/BoR	Molecularly eligible centrally confirmed evaluable for response set Evaluable for response set Interim analysis set i

Outcome Variable	Analysis Set
Duration of radiological response	Molecularly eligible centrally confirmed evaluable for response set Evaluable for response set‡ Interim analysis set I
rPFS	Molecularly eligible centrally confirmed set Safety set Interim analysis set I
PSA	Molecularly eligible centrally confirmed set Safety set* Interim analysis set I
CTC conversion	Molecularly eligible centrally confirmed evaluable for response set Evaluable for response set* Interim analysis set I
CCI	
CCI	CCI
Safety Data	
Exposure	Safety set
AEs	Safety set
Laboratory measurements	Safety set
Vital signs	Safety set
Physical examination	Safety set
Eastern Cooperative Oncology Group performance status (ECOG PS)	Safety set

\* CCI

‡ Only swimmer plot will be provided for this analysis set.

◊ Only spider plot will be provided for this analysis set.

IThis analysis set will be used only for interim analysis summary.

## 4.6 Study Participants

### 4.6.1 Disposition of Participants

Disposition of all participants who enter the study will be summarised for all enrolled participants. The number and percentages of participants will be presented for the following categories:

- Enrolled (including the screen failures)

- Participants assigned to treatment
- Participants not assigned to study treatment (and reason)
- Received study treatment
- Did not receive study treatment (and reason)
- Participants ongoing with study treatment at data cut off (DCO)
- Participants ongoing in the study at DCO.
- Discontinued from study treatment (and reason)
- Prematurely withdrawn from study (and reason)

Additional listings and summaries on participants affected by the COVID-19 pandemic will also be presented as per standards.

#### 4.6.2 Protocol Deviations

Important protocol deviations (IPDs) are defined as those deviations from the protocol likely to have heavy impact on the interpretation of any analysis based on addressing the primary and secondary objectives of the trial or those may significantly affect a subject's rights, safety or wellbeing.

The following general protocol deviation categories will be programmatically derived from the electronic case report form (eCRF) data. These deviations will be reviewed and assessed on a case-by-case basis by AZ to determine importance. Deviations considered to be important will be listed and discussed in the CSR as appropriate. All decisions on importance will be made ahead of database lock for the primary analysis and will be documented prior to the primary analysis being conducted. Additional non-programmable protocol deviations identified during site visits will be listed as an appendix in the CSR. All IPDs as per the latest PD specifications, not limited to the following will be summarised and listed separately for each module, by cohort and by starting dose of ceralasertib.

- Participants who deviate from inclusion /exclusion criteria per the Clinical Study Protocol (CSP).
- Participants who fail to sign the correct informed consent form for both screening part 1 and part 2, except the genetic informed consent form.
- Participants whose baseline efficacy assessments as per CSP are missing.
- Participants whose baseline safety assessments as per CSP are missing.
- Participants who used disallowed concomitant medications.
- Participants who received prohibited medications during the study. Refer to the CSP Section 6.5 for those medications that are detailed as being 'excluded' from permitted use during the study. This will be used as a guiding principle for the physician review of all medications prior to database lock.
- Participants who received not per protocol (incomplete/overdose) study treatment.
- Study treatment was not given according to protocol.
- Participant has not a histologically confirmed diagnosis of AST (excluding NSCLC) or mCRPC tumour.

- Tumour does not contain a deleterious ATM mutation, tested on a tumour specimen or circulating tumour DNA tested in a locally accredited laboratory using a validated test in line with local regulations.
- Participants with more than 28 days of study drug interruption.
- Persistently missing important protocol required post-baseline safety assessments (vital signs, clinical chemistry/haematology parameters, Hy's Law assessments etc.) and potentially having major impact to participant's safety.
- Baseline RECIST 1.1 scans missing or > 28+ days before treatment assignment.
- Baseline bone scans missing or > 28+ days before treatment assignment.
- Met study treatment discontinuation criteria (e.g., The pregnancy test was positive) however participant was not withdrawn from study treatment but continued study treatment and potentially had major impact to participants' safety according to clinical judgement.
- Persistently missing important post-baseline protocol required efficacy assessments (soft tissue disease progression as defined by RECIST 1.1, bone lesion progression by PCWG-3, radiological progression, CTC count, PSA).

The following will be checked for analysis purposes and will not be included as part of the deviations to be recorded in the protocol deviations log during the study:

- Participants allocated to a treatment but who did not receive any study treatment

During the study, decisions on how to handle errors in treatment dispensing (with regards to continuation/dose reductions/discontinuation of study treatment or, if applicable, analytically) will be made on an individual basis with written instruction from the study team leader and/or statistician.

IPDs related to COVID-19 will be summarised as well.

A per-protocol analysis excluding participants with specific important protocol deviations is not planned, however a sensitivity analysis may be performed on the key efficacy endpoints if > 10% of participants in any treatment cohort have any other significant deviation deemed to affect the primary endpoint which haven't already led to exclusion from efficacy analysis.

The need for such a sensitivity analysis will be determined following review of the protocol deviations ahead of database lock and will be documented prior to the analysis being conducted.

### 4.6.3 Demographic and Other Baseline Characteristics

#### Module 1

Demographic and other baseline disease characteristics will be summarised and listed for safety set by cohort and by starting dose of ceralasertib.

- Demographics (age [years], age group [18-64 years; 65-84 years; ≥ 85 years], sex [Cohort A], sex [Cohort B: males only], race and ethnicity).
- Participant characteristics at baseline (height [cm], weight [kg], and body mass index [BMI in kg/m^2]).

- Previous disease-related treatment modalities.
- Number of regimens of previous chemotherapy
- Disease characteristics at baseline (Eastern Cooperative Oncology Group Performance Status [ECOG PS], primary tumour location, histology type, tumour grade, overall disease classification (local, metastatic, etc), Gleason score [only for Cohort B], CTC count [Cohort B]), CTC status [Cohort B: favourable, unfavourable] ATM mutation [type of mutation, Zygosity], ATM IHC [%]), TNM stages, number of metastatic sites, prior lines of anti-cancer therapies).
- Extent of disease upon entry ([metastatic or locally advanced disease], site of local/metastatic disease, days from recent progression to first day of study treatment)

#### 4.7 Medical and Surgical History

Disease related medical history and relevant surgical history will be coded using Medical Dictionary for Regulatory Activities (MedDRA) by system organ class (SOC) and preferred term (PT). All disease related medical history and surgical history (past and current) will be listed, the number and percentage of participants with any medical history will be summarised for safety set by cohort and by starting dose of ceralasertib. Additionally, surgical history will be summarised only for Cohort B safety set.

#### 4.8 Concomitant and Other Treatments

Information on any treatment that the participant is receiving at the time of enrolment and all concomitant treatments given up to 30 ( $\pm 7$ ) days after discontinuation of study treatment, with reasons for the treatment, dates of administration and the dosage will be recorded in the eCRF. See Section 11.6.5 and Appendix D of CSP for a list of allowed and prohibited medications and anti-cancer treatments for Module 1.

Treatments (including surgery, received prior to, concomitantly, or post-treatment will be coded using the World Health Organisation (WHO) Drug Dictionary (WHODD) Anatomical Therapeutic Chemical (ATC) classification codes. Concomitant medications will be summarised by ATC classification codes.

For the purpose of inclusion in prior and/or concomitant medication or treatment summaries, incomplete medication or treatment start and stop dates will be imputed as detailed in [Section 4.3.3.1](#) and [Section 4.3.3.2](#).

- Prior medications are those taken prior to study treatment with a stop date prior to first dose of study treatment.
- Concomitant medications are those with a stop date on or after the first dose date of study treatment (and could have started prior to or during treatment).
- Post treatment medications are those with a start date after the last dose date of study treatment.

Summaries of all allowed and disallowed concomitant medications with a start date on or before first dose of study treatment and up to the date of last dose of study treatment (inclusive) will be produced.

The number and percentage of participants who took any previous disease-related treatments will be summarised by therapy class (i.e., immunotherapy, hormonal therapy, cytotoxic chemotherapy, systemic therapy, radiotherapy etc.).

The number and percentages of participants with and without prior line of therapies will be provided. Summary statistics will also be provided for the number of regimens of previous chemotherapy.

Missing coded terms will be listed and summarised as “Not coded”.

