		
Section 1.1.1
 
Deletion of text “ensuring at least 60% of participants with ATM IHC <math>\leq</math> 5%”
 
Replaced Figure 1 and updated the footnotes to match CSP 3 Cohort B
 
Replaced Figure 2 and updated footnotesto match CSP3
 
Section 3.2
 
Interim Cohort A
 
Deletion of text “ensuring at least 60% of participants with ATM IHC <math>\leq</math> 5%”
 
Interim Cohort B
 
Deletion of text “ensuring at least 60% of participants with ATM IHC <math>\leq</math> 5%”
 
Section 4.2
 
Revised the general presentation guidelines for treatment group by assigned starting dose rather than starting dose.
 
Section 4.8
 
Updated the language to specify that allowed and disallowed concomitant medications those are ongoing or starting on or after the first dose of study treatment and up to the date of last dose of study treatment will be summarized.
 
Section 4.15
 
Added ATM mutation subcategories and CCI [REDACTED] to the subgroup analysis.
 
Section 4.17.2
 
Added the paragraph to explain how percentage change from baseline in target lesions waterfall plot will be plotted for ATM mutation CCI [REDACTED] subcategories.
 
Section 4.17.3
 
Added ‘time to progression’ swimmer plot.
 
Section 4.19.1.1
 
Updated the section with conditions to accommodate the 14 days on and 14 days off dosing schedule
 
Section 4.19.1.2

--	--	---

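### SAP Section 4.8: the start-date rule for the concomitant-medication summaries is inconsistent with itself and with the section's definition; read literally, it drops drugs first started from Day 2 to last dose

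*SAP*

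**What the plan says.** All of the following is in SAP Section 4.8 unless stated otherwise.

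- **Definition.** "Concomitant medications are those with a stop date on or after the first dose date of study treatment", with the added remark that they "and could have started prior to or during treatment".
- **Post-treatment class.** "Post treatment medications are those with a start date after the last dose date of study treatment".
- **Selection rule.** The summaries of allowed and disallowed concomitant medication are to cover those "with a start date on or before first dose of study treatment and up to the date of last dose of study treatment (inclusive".
- **Coding level.** "Concomitant medications will be summarised by ATC classification codes". This sentence sets no date window.

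Elsewhere, Tables 5 and 6 assign concomitant medications, procedures and radiotherapy to the safety set, also without a window. Section 4.6.2 lists "Participants who used disallowed concomitant medications" among its deviation categories. Section 4.3.3.2 leaves the end date blank for a record with no end date that is flagged as ongoing.

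**The concern.** The selection rule is the only sentence in Section 4.8 that sets a start-date window for these summaries, so a programmer has to apply it. Its first limit shuts out drugs begun after the day of first dose. The definition a few lines above lets them in.

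Drugs begun on treatment are the ones a reader most needs from this table. They include supportive care given for toxicity and any disallowed drug taken while on study. In open-label cohorts without a comparator, that information helps in interpreting adverse events and responses. A table that holds only drugs already in use by the day of first dose would not show it.

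**Working it through.** No arithmetic on trial figures applies, and the plan states no figure here to reproduce. The check sorts each kind of medication record under each possible reading of the rule.

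**Notation.** *S* = start date, *E* = stop date, *F* = date of first dose, *L* = date of last dose, with *F* ≤ *L*.

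**Conditions in Section 4.8**

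- Concomitant: *E* ≥ *F*; *S* may fall before or during treatment.
- Post-treatment: *S* > *L*.
- Selection rule, two limits: *S* ≤ *F*, and *S* ≤ *L*.

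**Reading 1: both limits must hold.** *S* ≤ *F* and *S* ≤ *L*. Because *F* ≤ *L*, this reduces to *S* ≤ *F*. The last-dose limit has no effect.

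**Reading 2: one range that begins before first dose and ends at last dose.** This reduces to *S* ≤ *L*. The first-dose limit has no effect.

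| Record | Meets concomitant definition? | Reading 1 | Reading 2 |
|---|---|---|---|
| Started and stopped before *F* | No (prior) | Out | Out |
| Started before *F*, still in use at *F* | Yes | In | In |
| Started on the day of *F* | Yes | In | In |
| Started from Day 2 to *L* | Yes | **Out** | In |
| Started after *L* | Yes by stop date, but also post-treatment | Out | Out |

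Three things follow.

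1. The readings differ in one row only: drugs first started from Day 2 to last dose. In that row Reading 1 contradicts the definition and Reading 2 agrees with it.
2. Under either reading one of the two limits is redundant. The sentence cannot be programmed without setting part of it aside.
3. The definition alone is not enough. A drug started after last dose has a stop date after first dose, so it meets both the concomitant and the post-treatment definitions. A last-dose limit on start date is needed to separate the two, and it has to be worded so that it does only that.

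**The case against.** The best case on the other side is that Reading 2 is plainly what was meant. It gives the last-dose limit a purpose, which is to remove post-treatment drugs, and it agrees with the definition. The revision history entry for Version 3.0 points the same way: it describes the Section 4.8 change as covering drugs "ongoing or starting on or after the first dose of study treatment and up to the date of last dose of study treatment". A change log cannot show that the current text is wrong, but it is fair evidence of intent, and it suggests a slip in wording and not a decision to leave out on-treatment drugs. This stands, and it limits the point to a wording conflict. It does not remove the conflict, because the operative sentence still names first dose as a limit on start date.

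A reader might go further and infer any of four stronger things. The SAP does not support them.

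- *That the plan omits every drug started on treatment.* This holds only under Reading 1, and even then a drug started on the day of first dose is kept.
- *That drugs stopped before first dose would enter the table.* The rule selects among concomitant medications, and the definition has already excluded those drugs.
- *That disallowed use would go unreported.* Section 4.6.2 makes disallowed and prohibited medication deviation categories, provides for physician review of all medications before database lock, and has important deviations summarised and listed. That safeguard is real but partial: it depends on a case-by-case judgement of importance and does not cover allowed drugs.
- *That nearly every participant is affected.* The SAP contains no figure on this.

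It can also be said that the sentence on ATC coding and Tables 5 and 6 carry no start-date limit. They carry no window of any kind, so they leave the conflict where it is.

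**Conclusion.** The point holds as an internal inconsistency in an operative rule. The start-date wording in Section 4.8 does not agree with itself or with the definition above it. Applied literally, it removes from the allowed/disallowed concomitant-medication summaries every drug first started from Day 2 to last dose.

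The consequence is limited to a descriptive summary on the safety set. No efficacy estimate, confidence interval, denominator or sample size is touched. How many records would be lost cannot be derived from the document.

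The conclusion rests on two assumptions: that the programmer follows the sentence as written, and that the separate table specifications named in Section 1, which are not available here, do not already resolve it. If they do, the SAP text should still be brought into line with them.

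**What to change.** Replace the selection wording with: *concomitant medications with a stop date on or after first dose (or ongoing/missing) and a start date on or before the date of last dose of study treatment*.

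In the notation above this is (*E* ≥ *F*, or ongoing/missing) and *S* ≤ *L*. It gives the Reading 2 column of the table: on-treatment starts are in, and prior and post-treatment drugs are out. It also deals with ongoing records, which have no end date to test under Section 4.3.3.2.

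Changing only *before* to *after* in the present sentence would not be enough. It would then drop drugs begun earlier and still in use at first dose, which the definition includes.

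The cost is one sentence in the SAP and a check that the table specifications match. No new data are needed, because Section 4.8 already has concomitant treatments recorded from enrolment until 30 (±7) days after discontinuation.
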